4.4.2 Baseline data

Baseline variables (from the 12 month period before 22 October 2018 and socio-demographic data from 12 month period after 22 October 2018) will be cross-tabulated to check for appropriate balance between study arms and to characterize the study population using summary statistics both at cluster and individual levels (Annex **Table 1, 2**).

Cluster (*i.e.* health center) level data will be collapsed across study arms and compared using mean, median and range with standard deviations and/or interquartile ranges as appropriate. The basis of this analysis will be data on demographics, health center and laboratory infrastructure, organizational hierarchy, Xpert referral network, and TB testing and treatment collected during site assessment, recruitment, and guidelines training.

Individual level data for all patients eligible for analysis will also be collapsed across study arms and compared using mean, median and range with standard deviations and/or interquartile ranges as appropriate. These individual factors include age, sex, HIV status, and ART status.

We will summarize data obtained during the pre-randomization period for the cohort of health centers and patients who are being enrolled in the study and randomized to a trial arm (Annex table 1).

We will also summarise of numbers referred for TB testing in intervention and control arms (collapsed over cluster) in the 12 month period after 22 October 2018 (Annex Table 3).

Descriptive data between control and intervention arms will be presented in tabular format in lieu of formal statistical comparison or significance tests, and will be reviewed to confirm comparability and identify any substantial imbalances. Adjusted effect estimates will be calculated by study arm to account for imbalance of covariates which are risk factors for the outcome of interest. Losses in degrees of freedom due to cluster-level covariate adjustments will be accounted for in all calculations.

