4.4.3 Primary analysis of primary outcome

Analysis will be conducted at the cluster (clinic)-level. The outcome is the count of the number treated for microbiologically-confirmed TB within two weeks of referral for sputum-based testing at the clinic-level. Initially Poisson regression will be used, with an offset at the clinic level of the total number of days the clinic contributes individuals to the study (starting from 22 October 2018). Evidence for over-dispersion will be assessed and if over-dispersion is detected then negative binomial regression will be used, using the same offset. Either model will adjust for randomisation strata and the count of microbiologically-confirmed TB cases that initiated on treatment within 14 days in the 12 month period before 22 October 2018. The exact functional form of this covariate will be identified through fractional polynomials. Further adjustment for clinic-level factors that show imbalance will be explored, though the number of adjustment factors will be limited as all are at the clinic-level. See Annex tables 4a and 4b, and 5a.

Xpert Ultra cartridges will be used in our intervention (see Outcomes Definitions Section 3.4). Two sensitivity analyses will be performed reclassifying 1) all trace-positive results as negative and 2) trace-positive results in HIV negative patients as true positive (even if not confirmed by a second positive test) to determine the impact of Ultra on the primary outcome. We expect to see trace-positive results in between 10-20% of all positive Xpert Ultra results, irrespective of study arm. Therefore, sensitivity analyses will only be done if the ratio of trace-positive results to all positive Xpert Ultra results is similar in both trial arms.

No sub-group analyses for strata defined at the individual-level (e.g., sex and HIV status) will be conducted as the primary outcome analyses are conducted at the cluster-level.

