4.4.4 Analysis of secondary outcomes

Secondary outcomes are reported as either counts, proportions, or time to event (continuous outcome), and are derived from data collected across routine data sources.

All analyses will adjust for randomisation strata. Intervention effect estimates will be reported for analyses (1) adjusting for randomisation strata only and (2) adjusting for randomisation strata and individual-level (proportions and time to event only) and clinic-level factors considered imbalanced, as outlined below. See Annex table 5b.

4.4.4.1 Count outcomes:

The analytic approach will be the same as described for the primary outcome. The outcome is the count of the respective outcome at the clinic-level. Analysis will be conducted at the cluster (clinic)-level. Either Poisson or negative binomial regression will be used, depending on over-dispersion. Adjustment will be made for the clinic-level count of the outcome using data in the 12 month period before 22 October 2018. The exact functional form of this covariate will be identified through fractional polynomials.

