4.4.4.2 Proportions

The analysis will give each cluster equal weight. The overall risk for each cluster will be calculated and shown, by strata and arm. A log transformation (where necessary) will be applied to the risk for each cluster. If a cluster has no events, 0.5 event will be added to all clusters in order that the log transformation can be conducted. The mean and standard deviation of these log risks will be used to obtain the geometric mean (GM) and associated 95% CI for each arm of the study. The risk ratio is estimated using linear regression of the log risks on stratum and arm. An approximate standard error for the difference in log (GM) between arms is obtained based on the residual mean square from a two-way analysis of variance (ANOVA) of the cluster log risk on stratum, study arm and the interaction between stratum and study arm. The 95% CI is calculated from this standard error, using a t-statistic with 16 degrees of freedom. This will be the primary analysis.

Limited adjustment for individual level factors is possible; age, sex, HIV status, and ART status. Adjustment, using a complete case analysis, will only be done if data completeness for the variable is more than 80% in both trial arms and imbalance is observed (not assessed through a P-value). Logistic regression will be used to adjust for any baseline imbalance at the individual level, adopting a two-stage approach. The regression model will include terms for the adjustment factors (individual level) and strata, but not study arm. For each cluster the fitted model will be used to obtain the ratio of observed to expected (O/E) events, and a log transformation will be applied to this ratio, where appropriate.

Linear regression of the log (O/E) on stratum and arm (2-way ANOVA) will be used to estimate the risk ratio. The variance for the ratio of mean O/E is calculated from the residual mean square from an ANOVA of log(O/E) on stratum, arm and the interaction between stratum and arm. The 95% CI is calculated from this variance, using a t-statistic with 16 degrees of freedom

If imbalance is observed for the equivalent cluster-level outcome in the 12 month period before 22 October 2018, adjustment at the second stage described above will be conducted, with appropriate adjustment for the degrees of freedom for the intervention effect. The exact functional form of this cluster-level covariate will be identified through fractional polynomials.

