4.4.4.1 *Time to event (continuous outcome)*

The analysis will give each cluster equal weight. The arithmetic and geometric mean for the continuous outcome of time to event (amongst all those experiencing the event) will be calculated for each cluster and shown, by strata and arm. A log transformation of the individual-level time to event will likely be necessary as the times to event may be positively skewed, resulting in geometric means. Clusters where no individuals contribute time to event outcome data will be excluded from the analysis.

ANOVA will be used to calculate either the difference in means between arms or geometric mean ratio, depending on whether a log transformation was used. This will be the primary analysis.

A two-stage approach, similar to as described above, will be used to adjust for confounders at the individual level. Limited adjustment for individual level factors is only possible; age, sex, HIV status, and ART status. Adjustment will only be done if data completeness for the variable is more than 80% in both trial arms and imbalance is observed (not assessed through a P-value). If imbalance is observed for the equivalent cluster-level outcome in the 12 month period before 22 October 2018, adjustment at the second stage described above will be conducted, with appropriate adjustment for the degrees of freedom for the intervention effect. The exact functional form of this cluster-level covariate will be identified through fractional polynomials.

4.4.5 *Sub-group analyses for secondary outcomes*

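### Counts are always adjusted for the clinic's own baseline value, but proportions and times only on an undefined imbalance: precision is probably lost and the adjusted column rests on judgement

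*Combined protocol and SAP*

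**What the plan says.** All references are to the current (amended) SAP.

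- **Primary count (4.4.3):** "Either model will adjust for randomisation strata and the count of microbiologically-confirmed TB cases that initiated on treatment within 14 days". These cases come from the year before the trial, and the adjustment is unconditional.
- **Secondary counts (4.4.4.1):** "Adjustment will be made for the clinic-level count of the outcome using data in the 12 month period before 22 October 2018". Also unconditional.
- **Proportions (4.4.4.2):** clinic log risks are regressed on stratum and arm, without the baseline value. The SAP then states: "The 95% CI is calculated from this standard error, using a t-statistic with 16 degrees of freedom. This will be the primary analysis". A further estimate brings the baseline value in only "If imbalance is observed for the equivalent cluster-level outcome in the 12 month period before 22 October 2018"; its shape is chosen by fractional polynomials.
- **Times (the section after 4.4.4.2):** ANOVA gives either a difference or a ratio, and the SAP describes the choice as "depending on whether a log transformation was used. This will be the primary analysis". The same conditional rule for the baseline value follows.
- **Reporting (4.4.4):** "Intervention effect estimates will be reported for analyses (1) adjusting for randomisation strata only and (2) adjusting for randomisation strata and individual-level". The second estimate also takes in clinic-level factors judged to be imbalanced. Table 5b prints both estimates with P-values.
- **Meaning of imbalance:** no size is given. The only gloss, for individual-level factors, is "imbalance is observed (not assessed through a P-value".
- **Degrees of freedom (4.4.2):** "Losses in degrees of freedom due to cluster-level covariate adjustments will be accounted for in all calculations".

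**The concern.** A clinic's baseline value sharpens the comparison because it predicts that clinic's later value, whether or not the arms happen to differ on it. Making its use depend on an observed difference gives up the gain in the balanced allocations, where it is available just as well. With 20 clinics, precision is scarce.

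The trigger also has no definition, so whoever judges imbalance decides what stands in the adjusted column of Table 5b. That person may already know the baseline data by arm: section 3.5 shows geometric means of 14.70 (control) and 6.49 (intervention) for the baseline count. That figure is for a count. It does show that stratifying and restricting on a percentage did not ensure balance on a related quantity.

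The SAP gives no reason for treating outcome types differently.

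**Working it through.** **The plan's own figure.** The SAP states no interval width or error rate for the adjustment rule. Its Table 3 can be reproduced: ratio = exp[(1.960 + z) × SD × √(2/n)], with n = 9 (ten clinics less the one added for stratification).

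- SD 0.2: exp(2.802 × 0.2 × 0.4714) = 1.302 and exp(3.242 × 0.2 × 0.4714) = 1.357
- SD 0.3: 1.486 and 1.582

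The table gives 1.30, 1.36, 1.49 and 1.58. With n = 10 they do not match. This supports a two-sided 5% level, which the SAP does not state outright.

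**Inputs from the SAP.** 20 clinics, 10 per arm; two strata of ten, cut at the median of the 2017 percentage treated within 14 days. The stratum-by-arm model leaves 20 − 4 = 16 df; one linear baseline term leaves 15.

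**Assumptions.** The correlation r (0 to 0.7), the trigger (a baseline difference above 0.25 or 0.5 SD), normal clinic-level values and a linear baseline term. Two cases bound the strata: (a) unrelated to the outcome's baseline; (b) cut on that same baseline.

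**Width.** At r = 0 the simulated ratio of mean widths, always adjusting over strata-only, is 0.9684/0.9319 = 1.039: the price of estimating one more term. For other r:

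- Case (a): ratio ≈ 1.039 × √(1 − r²). This gives 0.99, 0.90 and 0.74 at r = 0.3, 0.5 and 0.7. Break-even: r² = 1 − 1/1.039² = 0.074, r = 0.27.
- Case (b): a median split leaves 1 − 2/π = 0.363 of the baseline variance within strata, so ratio ≈ 1.039 × √[(1 − r²)/(1 − r² + 0.363r²)]. This gives 1.02, 0.98 and 0.89. Break-even: r = 0.42.

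**Simulation** (20,000 to 40,000 null trials per setting; estimate from stratum and arm, residual mean square from the model with interaction):

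| r | Case | Width ratio, always / strata-only | Error of trigger as sole rule (0.25 / 0.5 SD) |
|---|---|---|---|
| 0 | a | 1.04 | 5.0% / 5.0% |
| 0.3 | a | 0.99 | 4.5% / 4.4% |
| 0.5 | a | 0.90 | 4.1% / 3.8% |
| 0.7 | a | 0.74 | 3.4% / 2.7% |
| 0.3 | b | 1.02 | 4.8% / 4.8% |
| 0.5 | b | 0.98 | 4.8% / 4.7% |
| 0.7 | b | 0.89 | 4.0% / 3.7% |

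- In the 40,000-trial runs, for r up to 0.7, strata-only rejects in 4.8-5.3% and always adjusting in 4.9-5.2%.
- Within allocations whose baseline difference exceeds 0.5 SD (SD across all clinics), strata-only rejects in about 8-10% at r = 0.5 and 13-17% at r = 0.7. Such allocations are about 28% in case (a) and 7% in case (b). With a within-stratum SD, case (b) gives about 7-8% and 9-10%.
- Calling a result significant if either reported estimate is significant gives about 6% at r = 0, rising to 8% at r = 0.7.

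**In ratio terms.** SD of log risk = √(k² + (1 − p)/(mp)) = √(0.36² + 0.933/(268 × 0.067)) = 0.426, from the SAP's k, m and p. In case (a) the 95% limits are the estimate multiplied or divided by exp(0.9326 × 0.426) = 1.49 for strata-only. With adjustment they become exp(0.8384 × 0.426) = 1.43 at r = 0.5 and exp(0.6933 × 0.426) = 1.34 at r = 0.7.

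**The case against.** The strongest defence is that the SAP does not use the trigger for its main analysis. The primary estimate for proportions and times is fixed in advance, both estimates are reported, and lost degrees of freedom are counted. A reader might infer that secondary error rates are inflated. The documents do not support that: the declared analysis holds about 5% on average, and the trigger used alone errs low. Inflation needs either reliance on strata-only after a clear imbalance, or a choice between the two columns. This objection stands.

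Second, the contrast with counts has some reason. A raw count carries clinic size, which a proportion divides out, and the baseline percentage treated within 14 days was already used for strata and restriction. This stands for that outcome, which lies nearer case (b). It does not cover the other proportions or the times.

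Third, high correlations may be out of reach. Take Poisson noise, a true between-clinic CV of 0.36, 8 to 18 baseline events in 12 months (6.49 and 14.70 in ten months, times 1.2) and 18 to 38 trial events (6.7% of 268, or of 11,283/20 = 564). Even perfectly stable clinic risk then gives r between √[0.1296/(0.1296 + 1/8) × 0.1296/(0.1296 + 1/18)] = 0.60 and √[0.1296/(0.1296 + 1/18) × 0.1296/(0.1296 + 1/38)] = 0.76. So r = 0.7 is near the ceiling for that outcome. Outcomes with more events may do better, sparser ones worse.

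**Conclusion.** The point holds as one of precision and of an unspecified rule. Under r of 0.5 to 0.7, always adjusting narrows intervals by about 2-11% in case (b) and 10-26% in case (a). Below r of about 0.3 to 0.45 it gains nothing and costs up to about 4% in width. Neither r nor an imbalance threshold is in the documents, so the size is conditional. Fractional-polynomial selection was not simulated.

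Three stronger readings should not be drawn. Not every proportion and time interval is wider than it need be, since that depends on r. The sub-group results in Table 5c cannot be included, because section 4.4.5 does not say how the baseline value enters them. The primary count outcome is untouched, since its model always includes the baseline count.

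**What to change.** In the proportion and time sections:

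1. For every outcome with a register-based baseline, regress the clinic-level log risk (or log O/E, or mean or log mean time) on stratum, arm and the baseline value of the same outcome, with t on 15 df.
2. Fix one form now: the log of the baseline value, with the SAP's 0.5-event rule extended to clinics with no baseline events. Delete the fractional-polynomial search in these sections.
3. Name this the primary estimate and report strata-only beside it, so that nobody chooses between columns afterwards.
4. Delete the imbalance condition for the baseline value.
5. List in advance the outcomes kept at strata-only because no comparable baseline exists or it is too sparse, for example traced deaths and RIF resistance.

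The cost is SAP wording, one degree of freedom of 16, and slightly wider intervals where r is low. The protocol has registers photographed back to January 2016, so most baselines should exist. They should be built from sources that match the trial period, because on-site GeneXpert machine data were not available before it. The amendment table records post-hoc analyses for the trial manuscript in August 2020; where results by arm have already been seen, the adjusted analysis should be labelled supplementary and not made primary.

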Number with RIF resistance detected by Xpert/number with RIF resistance confirmed by culture*	Number with RIF resistance detected by Xpert/number with RIF resistance confirmed by culture	None
Proportion with RIF resistance detected by Xpert/proportion with RIF resistance confirmed by culture*	Number with RIF resistance detected by Xpert/number with RIF resistance confirmed by culture	Number enrolled
Time to microbiologically-confirmed TB**	Time-to-diagnosis if microbiologically-confirmed TB	None
C. Treatment		
Outcome	Numerator	Denominator
Number treated for TB*	Number treated	None
Proportion treated for TB*	Number treated	Number enrolled
Number treated for microbiologically-confirmed TB*	Number diagnosed AND treated	None
Proportion treated for microbiologically-confirmed TB*	Number diagnosed AND treated	Number enrolled
Proportion with microbiologically-confirmed TB treated*	Number diagnosed AND treated	Number diagnosed
Time-to-treatment of microbiologically-confirmed TB	Time-to-treatment if microbiologically-confirmed TB and treated	None
D. Follow-up		
Outcome	Numerator	Denominator
Number with microbiologically-confirmed TB completing treatment	Number diagnosed AND completing treatment	None
Proportion with microbiologically-confirmed TB completing treatment	Number diagnosed AND completing treatment	Number diagnosed AND treated
Number who died within 6 months	Number died	None

Proportion who died within 6 months***	Number died	Number enrolled
Number who died within 6 months	Number diagnosed AND died	None
Proportion who died within 6 months***	Number diagnosed AND died	Number diagnosed
Number who died within 6 months	Number treated AND died	None
Proportion who died within 6 months***	Number treated AND died	Number treated

*Outcome will be assessed within 1 day and within 14 days of enrolment. One day was chosen because the intervention focuses on same-day diagnosis and treatment. 14 days was chosen because the diagnostic process could take 7-10 days in the control arm depending on the frequency of sample transport to Xpert testing sites.

**For the control arm, missing Xpert result dates will be recorded as the next scheduled date of sputum transportation from the health center to the GeneXpert facility (results from the previous batch of testing are returned when the next batch of samples are picked up). For the intervention arm, missing Xpert result dates will be recorded as the day following sample collection.

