3.5 Sample Size

Sample size

Based on pre-randomization data collected from January to December 2017, we estimate 5360 patients will be enrolled across 20 study sites over the 18-month enrolment period. Other study intervals ranging from 12 to 24 months are considered.

Justification

Original detectable effect size estimates: The study is based on the health center being the unit of randomization and aims to demonstrate the superiority of the intervention arm. The sample size calculation uses formulae appropriate for cluster-randomized trials with a parallel design and stratified and/or restricted randomization, including the addition of one extra cluster per arm to allow for the loss of degrees of freedom due to stratification to obtain conservative estimates.⁷ The original detectable effect size estimates were based on the outcome being the proportion of patients treated for microbiologically-confirmed TB within two weeks of referral for sputum-based testing. A type I error of 5% and power of 90% was assumed. Pre-randomization data collected from January to December 2017 from the 20 selected trial sites in Uganda suggested that the average proportion of patients referred for TB evaluation who initiate treatment for active TB within two weeks would be 6.7%, and the coefficient of variation (k) between clusters is 0.36, with a harmonic mean of 268 patients enrolled at each health center cluster during the 18-month enrolment period. Based on these assumptions and assuming a type I error of 5%, we will have 90% power to detect a 6% or greater absolute increase in the outcome proportion in the intervention arm (see **Table 1**). Table 1 also shows detectable absolute effect sizes with varying power (80%, 85%, 90%) during various trial time intervals and respective average cluster size estimates.

[figure not shown]

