The minimum detectable effect size is based on published literature, our preliminary data demonstrating the increased sensitivity of Xpert Ultra vs. smear microscopy (95% vs. 40%), and reduced pre-treatment loss to follow-up expected in the intervention vs. control arms due to rapid, onsite molecular testing (7% vs. 30%). When applying these parameters to a population of 1000 individuals with TB prevalence of 10%, we would expect 95 patients to be diagnosed with TB and 88 to start treatment within 14 days in the intervention arm, and 40 patients to be diagnosed with TB and 28 to start treatment within 14 days in the control arm. Thus, the expected difference in the primary outcome proportion would be 8.8% vs. 2.8%, or 6%.⁸

Table 1. Absolute difference in the proportion of clinic attendees initiating TB treatment within 14 days of initial sputum submission, among those referred for TB testing

Average cluster size	Effect size (10 clusters per arm, $k=0.36$)		
	80% Power	85% Power	90% Power

178 (12 months)	5.9%	6.5%	7.4%
223 (15 months)	5.7%	6.3%	7.1%
268 (18 months)	5.5%	6.1%	6.9%
312 (21 months)	5.4%	6.0%	6.7%
357 (24 months)	5.3%	5.9%	6.6%

Figure 1. Effect size by cluster size. Number of clusters per arm is 10, $k=0.36$.

The primary outcome was changed to a count of the number of adults diagnosed and treated with TB at the cluster-level. The new primary outcome better reflects the intended effect of the multi-component intervention to drive more people who present to health facilities through the entire TB diagnostic evaluation cascade of care, including being screened for TB, tested for TB (if screen-positive), diagnosed with TB (if tested) and initiated on treatment (if diagnosed). Process re-design is expected to help improve the number screened and tested. Onsite molecular testing is expected to increase the numbers diagnosed (increased sensitivity) and treated (faster turn-around time and reduced workload). Performance feedback is expected to maintain improvement along each step of the cascade. Thus, the intervention is expected to increase both the number of patients entering and completing the cascade of care.

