Pre-specified sub-group analyses for a subset of secondary outcomes will be conducted to assess whether the effect of the intervention differs between sub-groups. The sub-groups are (1) HIV status at enrolment (self-reported, laboratory test resulted as noted on primary data sources, or through pre-ART and ART register data extraction) defined as positive or negative, and (2) sex (male or female). The effect of the intervention will be estimated for each sub-group, and P-values for effect modification, appropriate for individual-level covariates, will be reported.¹⁰ These sub-group analyses will be conducted for the following secondary outcomes: proportion completing testing; proportion of patients referred for TB testing who are diagnosed with microbiologically-confirmed TB within 14 days; proportion of patients with microbiologically-confirmed TB who are treated within 14 days of referral for sputum-based testing; and the proportion who died within 6 months. See Annex table 5c. Results from subgroup analyses will also be summarised as forest plots.

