B. Proportion referred for TB testing who are diagnosed with microbiologically-confirmed TB (by day 14)							
HIV-positive	% (n/N)						
HIV-negative	% (n/N)						
Male	% (n/N)						
Female	% (n/N)						
C. Proportion of patients with microbiologically-confirmed TB who are treated within 14 days of referral for sputum-based testing							
HIV-positive	% (n/N)						
HIV-negative	% (n/N)						
Male	% (n/N)						
Female	% (n/N)						
D. Proportion who died within 6 months							
HIV-positive	% (n/N)						
HIV-negative	% (n/N)						
Male	% (n/N)						
Female	% (n/N)						

Figure 1: Comparison of TB diagnostic evaluation in the intervention and control arms

[figure not shown]
[figure not shown]

Figure 2: CONSORT diagram

CONSORT diagram will be constructed show individual and cluster-level data at baseline and follow-up and based on the CONSORT extension to CRTs.

Post-hoc analyses

The following outcomes were not specified in the SAP but were included in the trial manuscript to ensure 1) each proportion outcome had a corresponding count outcome (or vice versa) and 2) every relevant step of the TB diagnostic evaluation cascade was represented (for those with microbiologically-confirmed TB).

Overall

- Number completing testing

Patients with microbiologically-confirmed TB

- Proportion diagnosed*

Subgroup analyses

- Number completing testing
- Number diagnosed with microbiologically-confirmed TB*
- Number treated for microbiologically-confirmed TB*
- Number treated for TB*
- Proportion with same-day diagnosis of microbiologically-confirmed TB
- Proportion with same-day treatment for microbiologically-confirmed TB
- Proportion treated for TB*

*Outcomes assessed within 1 day and within 14 days of initial sputum submission

References

3. Ministry of Health (Republic of Uganda). Health Facilities Inventory. Department of Clinical Services. Kampala, Uganda 2012:140.
4. Uganda Bureau of Statistics. The National Population and Housing Census 2014 - Main Report. Kampala, Uganda 2016.
5. Uganda Bureau of Statistics. National Population and Housing Census 2014 - Provisional Results. Kampala, Uganda 2014.

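### Three six-month mortality proportions share one label while the tables carry one unlabelled version, and those among diagnosed and treated patients are not randomised comparisons

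*Combined protocol and SAP*

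**What the plan says.** In the current SAP, section 3.4 (Secondary Outcomes, D. Follow-up) has three rows for the proportion who died within six months, all with the same label. The first divides deaths by the number enrolled. The second has the numerator "Number diagnosed AND died" over the number diagnosed. The third has "Number treated AND died" over the number treated. Three count rows also share one label.

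Section 4.4.5 ends its list of sub-group outcomes with "and the proportion who died within 6 months. See Annex table 5c". Table 5c has one mortality block, "D. Proportion who died within 6 months". Table 5b has one count row and one proportion row for death. None of these gives a denominator, although blocks B and C of Table 5c do give theirs.

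Section 4.4.1 commits to comparing all effectiveness outcomes between arms. Section 4.4.4 commits to intervention effect estimates for the secondary outcomes, so the diagnosed and treated versions are due a risk ratio, a confidence interval and a P-value.

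**The concern.** There are two problems, and the second matters more.

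First, a reader of Table 5b, section 4.4.5 or Table 5c cannot tell from the current text which mortality proportion is reported.

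Second, diagnosis and treatment happen after randomisation, and section 3.5 states that the intervention is expected to increase both. The diagnosed patients in the intervention arm would include cases that smear would have missed, and the control arm has no matching group in its denominator. If those cases differ in their risk of death, the planned risk ratio moves away from 1 even when nobody's survival changes. A fall could be read as lives saved, and a rise as harm. Mortality is likely to be read as the most consequential of the secondary outcomes, so a spurious result in either direction would carry weight.

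**Working it through.** **Inputs from the SAP (section 3.5).** Test sensitivity 95% versus 40%; loss before treatment 7% versus 30%; 1000 people evaluated, 10% with TB; 268 patients per clinic; 10 clinics per arm. No death rate or power is given for mortality: "A type I error of 5% and power of 90% was assumed" refers to the proportion treated within two weeks. All death risks below are therefore assumptions.

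**1. Reproduce the SAP's illustration, per 1000.**
- Diagnosed: 1000 × 0.10 × 0.95 = 95; 1000 × 0.10 × 0.40 = 40.
- Treated: 95 × 0.93 = 88.35 (stated as 88); 40 × 0.70 = 28.
- Ratio of denominators: 95/40 = 2.4 for diagnosed; 88/28 = 3.1 on the stated counts.

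**2. Among diagnosed, with no survival effect.** Let the 95 − 40 = 55 Xpert-only cases carry *f* times the death risk of the smear-detectable cases. Then RR = (40 + 55*f*)/95.
- *f* = 0.5: 67.5/95 = 0.71
- *f* = 1: 1.00
- *f* = 1.5: 122.5/95 = 1.29

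Equivalently, RR − 1 = (1 − *s*)(*f* − 1), where *s* is the control yield divided by the intervention yield, here 40/95 = 0.42. The distortion shrinks in proportion as *s* approaches 1.

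**3. Among treated.** Assume that loss before treatment is unrelated to the risk of death. The intervention arm then treats 40 × 0.93 = 37.2 smear-detectable and 55 × 0.93 = 51.15 Xpert-only cases. RR = (37.2 + 51.15*f*)/88.35, which is again 0.71 at *f* = 0.5 and 1.29 at *f* = 1.5. The factor *f* belongs only on the Xpert-only cases: 37.2 − 28 = about 9 of the additional treated patients are smear-detectable people kept through lower loss.

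**4. Among enrolled.** With equal enrolment the RR is 1.00. If the intervention arm enrols 25%, 50% or 100% more people (assumed) and the extra people have no deaths, the RR is 1/1.25 = 0.80, 1/1.5 = 0.67 or 1/2 = 0.50. If they have the same risk as the rest, the RR stays at 1.00. The count of deaths behaves the other way: unchanged if the extra people have no deaths, and up by 25%, 50% or 100% if they have the same risk, because deaths are counted only among enrolled patients. The two are therefore best read together.

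**5. Behaviour under the planned analysis.** The section 4.4.4.2 method was simulated 3,000 times per row with no survival effect. Settings: 268 patients and 27 TB cases per clinic, the sensitivities above, an assumed between-clinic SD of log risk of 0.2, and an assumed 2% death risk without TB.

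| Assumed risk, smear-detectable | *f* | Diagnosed: median RR | P<0.05 | Enrolled: median RR | P<0.05 |
|---|---|---|---|---|---|
| 10% | 0.5 | 0.63 | 28% | 1.01 | 5% |
| 10% | 1 | 0.86 | 7% | 1.00 | 5% |
| 10% | 1.5 | 1.10 | 6% | 1.00 | 4% |
| 20% | 0.5 | 0.69 | 24% | 0.99 | 4% |
| 20% | 1 | 1.00 | 3% | 1.01 | 4% |
| 20% | 1.5 | 1.29 | 13% | 1.00 | 5% |

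At 10% risk the diagnosed ratio is pulled further down, even at *f* = 1. The rule of adding 0.5 event to every clinic weighs more on the small control denominators (27 × 0.40 = about 11 per clinic).

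**The case against.** **The three outcomes are pre-specified and the unlabelled one has a history.** Section 3.4 defines the three death counts under distinct names, and section 4.4.1 commits to comparing all outcomes. In the protocol and SAP version 1.0 the only mortality proportion was over the number enrolled. The sub-group entry and the Table 5c block carry over from there, and the amendment log records additional mortality outcomes on 21 November 2019. The 12 July 2021 entry describes the number enrolled as the full study population. This largely stands. A reader might infer that the sponsor is free to pick the most favourable of three proportions after seeing the data, with an inflated false-positive rate. The documents do not support that: they call for all three to be compared, and the likeliest reading of the single row is enrolled. Nor is any mortality contrast a deciding one, because the primary outcome is a treatment count. What remains is that the current text never states the denominator. Reporting all three also does not help, since it is what produces effect estimates within groups formed after randomisation.

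**The illustration exaggerates the gap.** It gives the control arm smear only, whereas controls also have hub Xpert, and HIV-infected patients give sputum for it at the first visit. Before randomisation 6.7% started treatment within two weeks, against 2.8% in the illustration's control arm. Its treated counts also stop at 14 days, which the mortality denominator does not. This stands: the size is upper-end. The direction of the argument is unaffected.

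**Deaths among confirmed or treated patients are informative.** They are, and should be reported. Presenting them as arm effects with P-values is what is not justified.

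**Conclusion.** The point holds as a labelling gap together with two planned arm comparisons that lack the protection of randomisation. On the SAP's own illustration and an assumed 0.5 to 1.5 times death risk in Xpert-only cases, the risk ratio is 0.71 to 1.29 among diagnosed with no survival effect, and about the same among treated. The range depends on the assumed *f* (at *f* = 1 the arithmetic gives 1.00), on a yield gap that is probably too wide, and, for treated patients, on loss being unrelated to risk.

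A reader might also infer that the enrolled proportion is clean. It is not. Section 3.5 expects more patients to enter the cascade, and the protocol's amendment table records more referrals in the intervention arm. Enrolled is the better choice because membership does not depend on a test result or on starting treatment. That it is less exposed assumes that the rise in enrolment, whose size the documents do not give, is smaller than the gap in diagnosed or treated patients.

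**What to change.** 1. In section 3.4, label the three proportions and their counts *among all enrolled*, *among confirmed TB* and *among treated*, and give each a row in Table 5b.
2. Name *among all enrolled* as the mortality proportion in Table 5b, section 4.4.5 and Table 5c.
3. Present it with the number enrolled per arm and the already-listed count of deaths per clinic, modelled with the clinic-time offset. That count needs no denominator formed after randomisation, but it covers only enrolled patients and should be read with that in mind.
4. Report the confirmed-TB and treated versions per arm as descriptive, with a statement that they are not randomised comparisons.

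The cost is wording in the SAP and its tables, with no new data. The downside is that any mortality effect is diluted among TB-negative patients in the enrolled contrast and so is harder to see.
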